7.1.2 Missing Data

MMRM is the best method to control type I error rate and minimize bias in the presence of missing data, although this does not fully overcome the issues and assumptions are still required to be made regarding the missing data mechanisms. Nevertheless, in the presence of a high drop out rate performance of sensitivity analysis is critical. The purpose of sensitivity analysis is to explore whether different analyses under different set of missingness assumptions provide robust efficacy results. The extent to which efficacy results are stable across such analysis provides confidence in the statistical conclusions.

Missing data can be considered to be missing completely at random (MCAR), missing at random (MAR), or missing not at random (MNAR) according to the National Academy of Sciences (2010).

To explore the effect of missing data the following sensitivity analyses will be conducted for the primary efficacy analysis for the FAS population. Under the assumption that missing data is missing at random and the analyses require the assumption of MAR to hold:

- Imputation based analysis
 - Multiple Imputation

Subjects with missing SKAMP total scores at any timepoint during Visits 6 and 7 will have these individual SKAMP total score values imputed.

Step 1: Imputation

For each missing SKAMP total score 20 imputations will be made using SAS PROC MI on the unimputed SKAMP total score efficacy data. All imputed data will be non-negative. For intermittent missing data the Markov Chain Monte Carlo (MCMC) simulation will be used, the number of burn in iterations will be set at 200, or higher if required for convergence. The thinning option will be set to select one out of every 100 iterations to ensure sufficient separation from previous iterations.

Once intermittent missing data has been imputed monotone missing data will be imputed using a regression model including factors for treatment and period and the SKAMP total score in the VAR statement.

The number of multiple imputations will be 20, leading to 20 completed data sets.

Step 2: Analysis of completed data sets

The imputed data for the primary endpoint will be analyzed as per the method described in section 7.1.1. This will lead to 20 estimates for the comparison of d-ATS with placebo.

Step 3: Inference

The estimates will be averaged and the associated standard errors will be summarized based on within-imputation and between-imputation variance, as is customarily done in multiple imputation. In other words, PROC MIANALYZE will summarize the 20 model estimates yielding a final estimate with associated 95% CI and p-value.

- LOCF

Subjects who started a classroom day but did not complete all the assessments will have their last observation within the same classroom day carried forward. Data from one classroom day will not be used to impute values for another test classroom day.

The completed LOCF data will be analyzed as per the method described in section 7.1.1.

The following sensitivity analyses will be conducted for the primary efficacy analysis for the FAS population under the assumption of some data MNAR:

- Worst-case scenario analyses

- Scenario One

Subjects with missing data which is considered due to a defined 'poor outcome' will have the worst case (largest) SKAMP total score for that subject within the same classroom day imputed. If no SKAMP total score is available for a subject in a classroom day the overall observed worst case (largest) SKAMP total score for the same treatment will be imputed. For subjects with missing data which is not considered due to the defined 'poor outcome' reasons the mean SKAMP total score per treatment will be imputed.

Poor outcome reasons are defined as missing data due to poor tolerability and withdrawal due to lack of efficacy, AE or death.

Poor outcome reasons will be reviewed on blinded data and defined prior to database lock.

- Scenario Two

Results of two analyses will be presented for comparison. The first will assign the best possible outcome to missing values in the placebo group and the second will assign the worst possible outcome to those of the d-ATS group.

Sensitivity analysis using different methods of handling missing data will provide useful information about effectiveness of the study drug and confidence in the reliability of the conclusions drawn.

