Subjects will be discontinued if they are unable to tolerate d-ATS or cannot reach their optimal dose by Week 5. If the subject has reached their optimal dose, then at the discretion of a medically qualified investigator, one dose reduction per participant may occur during the dose optimization period for safety reasons. However if the current dose is intolerable and the subject has never reached their optimal dose, the subject would be discontinued from the study. A dose increase may occur at visit 4 if no prior dose has met criteria for optimal response and the current dose is well tolerated as deemed by a medically qualified investigator. The dose used during the week 5 visit will be the dose that the subject is randomized to during the Double-Blind Treatment Period. During Visit 5, subjects will attend a half-day practice laboratory school with analog classroom sessions to become familiar with classroom schedules and procedures. Three SKAMP assessments will be performed, and 3 practice PERMP tests will be given during the practice session.

Double-Blind Treatment Period [Day 36 to Day 49; Visit 6 (Day 42) and Visit 7 (Day 49)]: Subjects who have reached an optimal dose will enter the two-week double-blind treatment period. Subjects will be randomized to receive daily d-ATS treatment (at the optimized dose) for one week followed by daily placebo patched (identical in appearance to d-ATS) for one week, or vice versa.

During Week 6 subjects will receive study patches in accordance with the randomization schedule and during Week 7 subjects will cross-over to receive the other study treatment per the randomization schedule.

Follow-Up: A safety follow-up will be conducted by telephone 7-10 days (Visit 8, Day 56) after last dose of study drug.

The duration of the study will be approximately 56 days for each individual subjects (not including screening and washout).

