3.1 SAMPLE SIZE CONSIDERATIONS

Assuming a standard deviation (SD) of [REDACTED] and based on an average difference in total SKAMP scores between Placebo and d-ATS of [REDACTED], 74 subjects would need to complete the study to detect a true difference of [REDACTED] in mean total SKAMP scores between placebo and d-ATS at 80% power when testing at a significance level of $\alpha = 0.05$ (2-sided). Assuming a dropout rate of 20%, 90 subjects will be randomized and it is expected that 74 subjects will complete the study. A subject will be considered to have completed the study if the subject received both treatments during the double-blind Treatment Period and have completed both 12-hour classroom sessions during the double-blind Treatment Period.

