3.2 RANDOMIZATION

Randomization will occur prior to the start of the double-blind study period. Subjects will be randomized to one of the two treatment sequences (d-ATS then Placebo or Placebo then d-ATS) in a 1:1 ratio. Each eligible subject will be randomized to group assignment by a centralized Interactive Voice Response System (IVRS) /Interactive Web Response System (IWRS). Randomization will be applied centrally, without any stratification factors, across all sites to ensure even distribution of subjects across each treatment sequence.

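### Scenario One assigns the worst score by reason for withdrawal, not by treatment worn, so a poor-outcome withdrawal before Visit 6 is penalised on both treatments whichever one failed

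*SAP*

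**What the plan says.** Scenario One (SAP 7.1.2) first asks whether data are missing because of a poor outcome. The trigger is one sentence: "Poor outcome reasons are defined as missing data due to poor tolerability and withdrawal due to lack of efficacy, AE or death". These reasons are to be reviewed blind and settled before database lock.

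Where the trigger applies and the classroom day is partly observed, the gaps take the child's own largest score that day. If there is no score for "a subject in a classroom day the overall observed worst case (largest) SKAMP total score for the same treatment will be imputed". Data missing for other reasons take the treatment mean.

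Four other provisions bear on this:

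- Children are allocated to d-ATS then placebo or the reverse (SAP 3.2), and "during Week 7 subjects will cross-over to receive the other study treatment per the randomization schedule" (SAP 3).
- The full analysis set keeps any randomised child who has taken a dose (SAP 6.1).
- The early termination procedures (Protocol 5.3.6) include no SKAMP, so there is no score for the visit mapping in SAP section 7 to carry forward.
- Scenario Two consists of two analyses. One gives missing placebo values the best possible outcome, and the other gives missing d-ATS values the worst possible outcome.

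**The concern.** A child who leaves in Week 6, before the Day 42 classroom, has one withdrawal reason and two empty days. If that reason is a poor outcome, the text fills both days with a maximum. A child who left d-ATS because of an adverse event receives the d-ATS maximum, and also the placebo maximum for a placebo week never started. A child who left placebo for lack of efficacy receives the same pair. The rule uses the reason for dropout but loses the one fact that gives the reason meaning in a crossover, namely which treatment was being worn.

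SAP 7.1.2 treats stability across sensitivity analyses as grounds for confidence in the conclusions. For these children, much of the stability under Scenario One comes from the imputation rule and not from the data. It can reassure too much after d-ATS failures, and it withholds benefit from d-ATS after placebo failures.

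**Working it through.** **Plan figures.** The documents give no figure for Scenario One. The sample size section states: "Assuming a dropout rate of 20%, 90 subjects will be randomized and it is expected that 74 subjects will complete the study". The SD and difference are redacted, so the 74 cannot be re-derived. The stated numbers imply 90 − 74 = 16 losses, or 16/90 = 17.8%. I use 16 only as an outer bound for k, because it covers both weeks, both treatments and all reasons.

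**Notation.** Benefit D is placebo mean minus d-ATS mean, so a positive value favours d-ATS. Let k of 90 children leave before Visit 6 for a poor outcome. The closed forms ignore period and sequence terms.

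- Scenario One as written, whichever treatment failed: [(90 − k)D + k(maxP − maxD)]/90.
- Worst score on the failed d-ATS day only, placebo day at its mean: [(90 − k)D + k(meanP − maxD)]/90.
- Penalty missed for d-ATS failures (the difference): k/90 × (maxP − meanP).
- Benefit missed for placebo failures, by the same step: k/90 × (maxD − meanD).

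**Direction.** If the maxima are equal, the estimate shrinks by exactly k/90: 2.2% for k = 2, 5.6% for k = 5, 8.9% for k = 8 and 17.8% for k = 16. If maxP exceeds maxD by more than D, the check raises the benefit. With D = 6, k = 5 and maxima of 60 (placebo) and 45 (d-ATS), (85 × 6 + 5 × 15)/90 = 6.50.

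**Size, first set of assumptions** (none from the documents): means 18 on d-ATS and 22 on placebo, so D = 4. Maxima are about 52 and 56, as simulated with SDs of 8 (child), 5 (day) and 6 (session). All k are d-ATS failures.

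| k | As written | d-ATS day only | Missed penalty |
|---|---|---|---|
| 1 | (89×4 + 4)/90 = 4.00 | (89×4 − 30)/90 = 3.62 | 34/90 = 0.38 |
| 2 | (88×4 + 8)/90 = 4.00 | (88×4 − 60)/90 = 3.24 | 68/90 = 0.76 |
| 8 | (82×4 + 32)/90 = 4.00 | (82×4 − 240)/90 = 0.98 | 272/90 = 3.02 |

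If all eight are placebo failures, the written rule again gives 4.00. The treatment-linked rule gives (82 × 4 + 8 × (56 − 18))/90 = 7.02.

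**Size, second set of assumptions:** placebo mean 22, D = 6, maxP = 60, k = 5. For maxD of 60, 55 or 45, Scenario One gives 5.67, 5.94 or 6.50, and penalising the d-ATS day only gives 3.56, 3.83 or 4.39. The gap is 5/90 × 38 = 2.11 each time.

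**Model check.** A simulation used a model of the SAP's form: independent residuals, with treatment-by-time, period and sequence terms. It had 60 runs per setting, k = 5, a post-dose effect of 8, and averaging over all ten sessions including pre-dose. The benefit was 7.04 (SE 0.43) on available data, 6.90 (SE 0.51) under Scenario One and 5.37 with only the d-ATS day penalised. The gap of 1.53 agrees with the closed form: the mean simulated placebo maximum was 49.75, and 5/90 × (49.75 − 22) = 1.54.

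**The case against.** **Scenario Two covers the main risk.** Its second analysis puts the worst possible outcome on missing d-ATS values with no matching placebo penalty. With the scale maximum of 78 and the first set of assumptions, k = 8 gives 4 − 8/90 × (78 − 18) = −1.33, a reversal and harsher than the 0.98 above. This stands, and it limits the defect to Scenario One. Scenario Two does, however, ignore why children left. Scenario One is the only missing-not-at-random check that uses the reason.

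**The numbers may be small.** Every randomised child has just reached a tolerated, effective open-label dose. About 45 children wear d-ATS in Week 6, so eight d-ATS failures would be 8/45 = 17.8% of them. This also stands: k = 8 is extreme, and k = 1 or 2 is the better guide to size.

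**Placebo failures are at least as plausible**, because Week 6 either continues an effective dose or switches to placebo. With one d-ATS and three placebo failures, the treatment-linked rule gives (86 × 4 − 30 + 3 × 38)/90 = 4.76 against 4.00 as written. The change is therefore not uniformly stricter.

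**The second day could be read as not due to the poor outcome.** The SAP does not say so, and that day is empty because of the same withdrawal. At the least, two programmers could code it differently. The planned final SAP version gives a route to settle it.

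**Conclusion.** The defect is real and confined to Scenario One. It concerns children in the full analysis set who withdraw for a poor outcome with no Visit 6 data. Each adds (placebo maximum − d-ATS maximum) to the benefit whichever treatment failed. Under the first set of assumptions the missed penalty is about 0.38 points for one d-ATS failure, 0.76 for two and 3.0 for an extreme eight. All point sizes rest on assumed means and maxima. The formula and its direction do not.

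The documents do not support four stronger readings that a reader might infer:

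- *The two days cancel exactly.* Each day takes its own treatment's maximum. The estimate stands still in the first example only because those maxima happen to differ by D. It shrinks by k/90 if they are equal, and can rise if they are further apart.
- *The whole worst-case set is uninformative, or the primary result is in doubt.* Scenario Two penalises d-ATS alone, and the primary analysis does not use this rule.
- *The correction would remove statistical significance.* At k = 8 under the treatment-linked rule, about 6% of simulations were significant by paired t-test on day means, but about 44% under an approximation to the planned session-level model. Neither rate should be relied on.
- *Every dropout is affected.* Other reasons take the treatment mean, and a child who leaves in Week 7 before Visit 7 has only the Week 7 treatment imputed.

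**What to change.** Before database lock, add to Scenario One that the worst score applies only to the classroom day of the treatment worn when the poor outcome occurred. That treatment follows from the withdrawal date and the randomised sequence, so the rule can be written now and applied after unblinding, while the review of reasons stays blind. State also that a double-blind week never entered is filled by the rule for data not missing through poor outcome, or by the multiple-imputation value. This wording also covers a child who leaves just after Visit 6 without starting Week 7.

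Report the number of poor-outcome withdrawals on each treatment, and read Scenario One alongside Scenario Two.

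The cost is one sentence in the SAP and one programming condition, with no new data and no change to the primary analysis. The sponsor should expect a result less favourable to d-ATS after d-ATS failures and more favourable after placebo failures.

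### The missing-not-at-random checks never combine best-placebo with worst-d-ATS, and the treatment-mean fill in Scenario One is analysed as if it were observed data

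*SAP*

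**What the plan says.** SAP section 7.1.2 (Missing Data) plans two sensitivity analyses under missing at random: multiple imputation with 20 data sets, and LOCF within a classroom day. Two more, both labelled worst-case, cover data missing not at random.

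- **Scenario One** is a hybrid. Scores missing because of poor tolerability, lack of efficacy, an adverse event or death get the child's own largest score that day. If that day has no score, they get the largest score observed on the same treatment. For all other missing scores, "the mean SKAMP total score per treatment will be imputed". No variance correction is described. The text does not say whether this mean is taken by timepoint or by period.
- **Scenario Two** is two analyses shown side by side. "The first will assign the best possible outcome to missing values in the placebo group"; the second gives missing d-ATS values the worst outcome. No run applies both. The SAP does not say whether the extremes are the scale limits or the observed extremes, or what happens to the other arm's missing values in each run.

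On the expected amount of missing data, SAP section 3.1 says: "Assuming a dropout rate of 20%, 90 subjects will be randomized and it is expected that 74 subjects will complete the study".

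**The concern.** These are the only analyses that leave the missing-at-random assumption, and section 7.1.2 itself calls sensitivity analysis critical when dropout is high. A worst-case check is useful because, if the result survives it, no pattern of missing values could overturn the result. Scenario Two cannot support that statement: each run stresses one arm and leaves the other alone. A report could show d-ATS ahead in both runs although the combined extreme puts it level or behind.

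In Scenario One, a filled mean is a guess that the model counts as a measurement. The point estimate hardly moves, the number of rows goes up, and the residual variance goes down, so uncertainty is understated for that part of the data.

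**Working it through.** **Inputs from the documents.** Ninety children are randomized in a two-period crossover and 74 are expected to complete, so 90 - 74 = 16 (17.8%) do not. SKAMP has 13 items scored 0 to 6 (SAP sections 4.1 and 5), so the total runs from 0 (best) to 13 × 6 = 78 (worst). The example code in section 7.1.1 uses a variance-components residual structure, which treats rows as independent.

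**The plan's own figure.** The SD and the difference are redacted, so the 74 cannot be rebuilt. The point does not contest it.

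**Assumptions.** Means and SDs below are illustrative because the design values are redacted. A missing day means all of one child's scores on one treatment. In the one-arm runs, the other arm's missing values are left at that arm's observed mean.

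**Scenario Two.** With m missing days per arm of 90, observed means P (placebo) and D (d-ATS), and negative differences favouring d-ATS:

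- placebo mean after the best fill = (90 - m) × P / 90
- d-ATS mean after the worst fill = [(90 - m) × D + 78m] / 90

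For P = 20, D = 14 and m = 8:

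- placebo: 82 × 20 / 90 = 18.22, so the first run gives 14 - 18.22 = -4.22
- d-ATS: (82 × 14 + 8 × 78) / 90 = 19.69, so the second run gives 19.69 - 20 = -0.31
- joint: 19.69 - 18.22 = +1.47

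The shifts from -6 are 1.78 and 5.69. They sum to 7.47, and -6 + 7.47 = +1.47.

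| Missing days per arm | Observed means | First run | Second run | Joint |
|---|---|---|---|---|
| 2 | 20 / 14 | -5.56 | -4.58 | -4.13 |
| 4 | 20 / 14 | -5.11 | -3.16 | -2.27 |
| 8 | 20 / 14 | -4.22 | -0.31 | +1.47 |
| 8 | 25 / 15 | -7.78 | -4.40 | -2.18 |

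A simulation of the planned model assumed SDs of 8 between children, 5 between days and 6 residual. It had 8 children each losing one day and a nominal 6-point effect (average available-data estimate about -5). d-ATS remained significantly better in about 100% of first runs, 71-80% of second runs and 44-53% of joint runs.

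**Scenario One, mean-filled part.** Take N planned rows per arm, residual SD s and a share p filled with the mean.

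- Available-data SE: s / √((1-p)N)
- SE after the fill: the residual variance falls to about (1-p)s² and the row count returns to N, giving s√((1-p)/N)
- Ratio: 1 - p

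If 16 of 90 children each lose one of two days and none is a poor outcome, p = 16/180 = 8.9% and the ratio is 0.91. The simulation also gave 0.91, and for 4, 8 and 18 children it gave 0.98, 0.96 and 0.90.

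**Scenario One as a whole.** With 16 affected children, the simulated SE relative to available data depends on the share with a poor outcome:

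| Poor-outcome share | 0% | 5% | 10% | 25% | 50% | 100% |
|---|---|---|---|---|---|---|
| SE ratio | 0.91 | 0.93 | 0.95 | 1.02 | 1.12 | 1.27 |

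Under these SDs the narrowing disappears at a share of roughly 20-25%.

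**The case against.** The SAP is open that Scenario Two is a pair of analyses for comparison, and each one leans against d-ATS. A reader can also approximate the joint estimate by adding the two shifts: in the example, -4.22 + (-0.31) - (-6) = +1.47. That stands for the point estimate. It does not supply a joint interval or p-value, and it works only if the other arm's missing values are handled as in the reference analysis, which the SAP does not state. With heavy missingness the second planned run may already give warning, as -0.31 does above. With very little, the joint run changes nothing important: two missing days per arm still leaves -4.13.

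On Scenario One, a reader might infer that its intervals are too narrow overall. The documents do not support that. Poor-outcome data get worst values, which add spread, and the poor-outcome share is not given. A reader might also put the 17.8% or 20% dropout into 1 - p and obtain 0.82 or 0.80. Those are shares of children, not of scores; the figures would need every non-completer to lose both classroom days and none to be a poor outcome. Nor should the ratio be turned into a coverage figure for this trial: that needs truly independent rows, and these are ten ratings a day on the same child.

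Finally, no decision rule depends on either scenario. The primary model, the multiple imputation, the LOCF analysis and the Completers analysis are unaffected, and the multiple imputation does carry imputation uncertainty under missing at random. All of that stands, and it keeps the point minor.

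**Conclusion.** The point holds in two limited parts.

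1. Scenario Two contains no joint worst case. The joint run is always at least as unfavourable to d-ATS as either planned run, and in the worked example with 8 missing days per arm it alone changes the sign. False reassurance is possible rather than shown; it depends on the number of missing days, the observed means and how the extremes are defined. Scenario One cannot stand in for the bound: a poor-outcome placebo dropout with no score that day receives the largest placebo score, which moves the comparison towards d-ATS.
2. The mean fill in Scenario One understates uncertainty for the values it fills, by a factor of about 1 - p in the standard error under the planned independent-residual model (0.91 at p = 8.9%). Whether the whole Scenario One interval ends up too narrow or too wide cannot be determined from the documents.

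This affects how far the sensitivity results can be trusted, not the primary result. The change is desirable rather than essential.

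**What to change.** **Scenario Two.** Add a third run with the best outcome for missing placebo values and the worst for missing d-ATS values in the same data set. State whether the extremes are 0 and 78 or the observed ones, and how the other arm's missing values are handled in the one-arm runs.

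**Scenario One.** Keep the worst-value rule for poor-outcome data. For the rest, replace the mean fill with the 20 planned imputation draws, made by timepoint and using treatment, period and the child's other scores. Analyse each completed data set with the section 7.1.1 model and combine with PROC MIANALYZE. Section 7.1.2 names treatment, period and the SKAMP total score for the imputation but not timepoint, so timepoint should be stated. This also settles a loose end: section 5 defines the mean SKAMP total score without the pre-dose session, while the model includes a pre-dose row that a missing day would need filled.

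**Cost.** A little programming before database lock, mostly reusing planned code, and wider sensitivity intervals. If few children have a poor outcome, the revised Scenario One will largely repeat the planned multiple imputation; the joint run is then the more informative addition.
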